8.1.10 Relationship Between Efficacy Endpoints

For the relationship of the change and percentage change from baseline (Week 0) to Week 12 of the treatment period between the efficacy endpoints, Pearson and Spearman correlation coefficients will be calculated, and scatter plots will be prepared. The combinations of endpoints to be evaluated are those for which a combination of diseases considered to be related (DU or DU-OAB) is specified in Figure 8-1.

Figure 8-1 Combinations of Efficacy Endpoints for Which the Relationship of Change and Percentage Change from Baseline (Week 0) to Week 12 of the Treatment Period Will Be Evaluated

		Pressure Flow Study						Uroflowmetry			
		BCI (males)	PIP1 (females)	Q _{max} (analyzed separately for males and females)	P _{det} Q _{max} (analyzed separately for males and females)	Duration of bladder contraction -1 (analyzed overall and separately for males and females)	Duration of bladder contraction -2 (analyzed overall and separately for males and females)	free Q _{max} (analyzed separately for males and females)	free Q _{ave} (analyzed separately for males and females)	Voided volume (analyzed overall and separately for males and females)	Voiding time (analyzed overall and separately for males and females)
Pressure Flow Study	BCI										
	PIP1										
	Q _{max}										
	P _{det} Q _{max}										
	Duration of bladder contraction-1	DU	DU								
	Duration of bladder contraction-2	DU	DU								
Uroflow- metry (uroflow metry)	free Q _{max}	DU	DU	DU	DU						
	free Q _{ave}	DU	DU								
	Voided volume	DU	DU	DU	DU	DU	DU				
	Voiding time	DU	DU	DU	DU	DU	DU				
Other Endpoints	Post void residual measured by ultrasonography	DU	DU	DU	DU	DU	DU	DU	DU	DU	DU
	BVE	DU	DU	DU	DU	DU	DU	DU	DU		DU
	IPSS total score	DU	DU	DU	DU	DU	DU	DU	DU		DU
	IPSS voiding symptoms score	DU	DU	DU	DU	DU	DU	DU	DU		DU
	IPSS (Question 1)	DU	DU	DU	DU	DU	DU	DU	DU		DU
	IPSS (Question 3)	DU	DU	DU	DU	DU	DU	DU	DU		DU
	IPSS (Question 5)	DU	DU	DU	DU	DU	DU	DU	DU		DU
	IPSS (Question 6)	DU	DU	DU	DU	DU	DU	DU	DU		DU
	IPSS storage symptoms score	DU-OAB	DU-OAB					DU-OAB			
Bladder Diary records	OABSS	DU-OAB	DU-OAB					DU-OAB			
	Average number of micturitions per 24 hours	DU-OAB	DU-OAB					DU-OAB			DU-OAB
	Average number of urinary urgency episodes per 24 hours	DU-OAB	DU-OAB					DU-OAB			
Average voided volume per urination		DU-OAB	DU-OAB					DU-OAB			DU-OAB

DU, relationship between endpoints for DU; DU-OAB, relationship between endpoints for DU improvement and OAB improvement

8.1.11 Analysis by Allocation Factor

- Analyses of secondary endpoints excluding analysis of covariance/analysis using an MMRM and scatter plots (8.1.1 to 8.1.9) will be performed by age group (< 65 years and \geq 65 years).
- Analysis will be performed as for analysis of secondary endpoints by sex (8.1.1 to 8.1.9). In analysis of covariance and analysis using an MMRM, values at baseline and age (< 60 years and \geq 60 years in males and < 70 years and \geq 70 years in females) will be used as covariates.

8.1.12 Analysis by Severity Score

The following analyses will be performed. The same analyses will be performed by sex.

- Analyses of the primary and secondary endpoints excluding analysis of covariance/analysis using an MMRM and scatter plots (7.3 and 8.1.1 to 8.1.9) will be performed by IPSS total score at baseline (Week 0).
- Analyses of the primary and secondary endpoints excluding analysis of covariance/analysis using an MMRM and scatter plots (7.3 and 8.1.1 to 8.1.9) will be performed by IPSS QOL score at baseline (Week 0).
- Analyses of the secondary endpoints excluding analysis of covariance/analysis using an MMRM and scatter plots (7.3 and 8.1.1 to 8.1.9) will be performed by OABSS score at baseline (Week 0).

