3. STUDY DESIGN

This study is a central-registration, multi-center, double-blind, placebo-controlled, randomized parallel-group comparative study to investigate the efficacy and safety of TAC-302 in DU patients with OAB. The design of this study is shown in [Figure 3-1](#). This study is composed of a single-blind observation period, a double-blind treatment period, and a follow-up period.

Patients considered eligible for the enrollment in the observation period after providing written informed consent will proceed to the observation period. The investigational drug for the observation period will be administered under single-blind conditions. In the observation period, the investigational drug (placebo) will be administered orally twice daily after breakfast and dinner for 2 to 4 weeks. Patients considered eligible for the enrollment in the treatment period after the end of the observation period will proceed to the treatment period. The investigational drug for the treatment period will be administered under double-blind conditions. The investigational drug in the treatment period will be randomly assigned, with patients allocated to the TAC-302 and placebo group in a 2:1 ratio. To maintain a balance between groups, dynamic assignment using assignment factors [sex (male and female), age at informed consent (< 65 years and \geq 65 years)] will be performed. In the treatment period, the investigational drug (TAC-302 200 mg or placebo) will be administered orally twice daily after breakfast and dinner for 12 weeks. After the start of the treatment period (registration in the treatment period), patients will make visits in weeks 2, 4, 8, and 12, and the designated observations and tests will be performed. A follow-up examination will be performed 1 week after the end of week 12 of the treatment period. If any adverse event is considered to be an adverse reaction after the follow-up examination, the follow-up investigation should be performed until it is confirmed that the symptom (including abnormal laboratory values) has recovered to the state of before the onset as much as possible or is resolving.

[figure not shown]

Figure 3-1 Study Design

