2.2 Target Sample Size

2.2.1 Target Sample Size

75 patients to be enrolled in the treatment period (48 males and 27 females)

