2.2.2 Rationale for the Sample Size

[REDACTED]

3. Data and Analysis Sets to Be Used for Statistical Analysis

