7.3 Secondary Analyses of the Primary Endpoint

For BCI (males) and PIP1 (females), the following analyses will be performed in the FAS and PPS.

- Time course plots at each evaluation time point (Weeks 0 and 12) will be prepared by group.
- Paired t-tests for the measured values at baseline (Week 0) and Week 12 of the treatment period will be performed by group.
- Summary statistics and 95% confidence intervals for the change and percentage change at Week 12 of the treatment period relative to baseline (Week 0) will be calculated by group.

- For the measured values at each evaluation time point (Weeks 0 and 12) and the change and percentage change from baseline (Week 0) to Week 12 of the treatment period, the 95% confidence interval for the difference between the placebo group and the TAC-302 group will be calculated.
- For the change and percentage change from baseline (Week 0) to Week 12 of the treatment period, student's t test will be performed using the placebo group as the control.
- Analysis of covariance of the change and percentage change from baseline (Week 0) to Week 12 of the treatment period will be performed using treatment group, baseline value, and age (< 60 years or \geq 60 years in males, < 70 years or \geq 70 years in females) as covariates, and the least squares means in each treatment group, and the difference in least squares mean between the placebo group and the TAC-302 group and its two-sided 95% confidence interval will be estimated.
- By age (< 60 years and \geq 60 years in males and < 70 years and \geq 70 years in females), the above analysis excluding time course plots and analysis of covariance will be performed.

8. Secondary Endpoint Analyses

The analyses of the secondary endpoints are outlined below.

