8.1.13 Analysis by Post Void Residual

The following analyses will be performed. The same analyses will be performed by sex.

- Analyses of the primary and secondary endpoints excluding analysis of covariance/analysis using an MMRM and scatter plots (7.3 and 8.1.1 to 8.1.9) will be performed by post void residual measured by ultrasonography (< 50 mL, \geq 50 mL, < 100 mL, and \geq 100 mL) at baseline (Week 0).

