11.8 Examination of Subgroups

In this study, subgroup analyses by allocation adjustment factors, severity score, and post void residual are planned in some analyses. Additional analyses will be performed as necessary.

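### The age, severity and post-void-residual subgroup analyses drop baseline adjustment and specify no estimate of whether the treatment effect differs between levels, so discordant p-values could be misread as effect modification

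*SAP*

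**What the plan says.** - **Age, primary endpoint (SAP 7.3).** BCI and PIP1 are re-analysed by age, cut at 60 years in men and 70 in women: "the above analysis excluding time course plots and analysis of covariance will be performed".
- **Age, secondary endpoints (SAP 8.1.11).** Split at 65 years, again without ANCOVA or MMRM.
- **Severity (SAP 8.1.12).** By IPSS total, IPSS QOL and OABSS at baseline: "Analyses of the primary and secondary endpoints excluding analysis of covariance/analysis using an MMRM and scatter plots". Each scale has three classes (SAP 6.1.1.3). The OABSS bullet names only secondary endpoints but also cites 7.3, so its scope is unclear.
- **Post void residual (SAP 8.1.13).** Cuts at 50 mL and 100 mL with the same exclusion. "The same analyses will be performed by sex", as is also the case in 8.1.12.
- **What remains in each level.** Summary statistics, paired t-tests within arm, the unadjusted between-arm difference with 95% CI, and Student's t-test against placebo. The bladder diary also keeps its rank tests and Fisher's test.
- **Interaction terms.** The only one in the SAP is treatment by time in the MMRM.
- **Interpretation.** SAP 11.8 says that "subgroup analyses by allocation adjustment factors, severity score, and post void residual are planned in some analyses" but gives no rule for reading them. SAP 11.5 treats multiplicity as not applicable.

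The omission is not uniform. The by-sex analysis of secondary endpoints in 8.1.11 keeps ANCOVA and MMRM with baseline as a covariate. No reason is given for dropping the adjusted models in the other subgroups.

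**The concern.** A subgroup analysis asks whether the effect differs between levels. Separate tests in each level do not answer that. With few patients, one level can reach significance and the other miss it although the true effect is the same in both. The quantity that addresses the question, the difference between the two effects with its interval, is not specified.

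Baseline adjustment is also dropped where the cells are smallest. Chance baseline imbalance is largest there, and precision is scarcest. At stake is how reliably subgroup results can be read. The primary analysis, which is descriptive (SAP 7.1), is unaffected.

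**Working it through.** **Inputs**
- Target of 48 men and 27 women, 75 in all (SAP 2.2.1; 48 + 27 = 75).
- Allocation (Protocol section 3): "with patients allocated to the TAC-302 and placebo group in a 2:1 ratio". This gives 32:16 men, 18:9 women and 50:25 overall.
- Effect size, SD and power are redacted (SAP 2.2.2), so the target of 75 cannot be re-derived. The standardised effect d, in SDs of change, is assumed over a range.
- No test level is stated. Two-sided 0.05 is assumed from the 95% intervals in SAP 7.3 ("its two-sided 95% confidence interval will be estimated").
- Subgroup prevalences are not given. Even splits are assumed.
- No dropout rate is given. Exclusions from the PPS would make cells smaller than those below.

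**Cells on an even split (TAC-302:placebo)**
- Men: 16:8 and 16:8.
- Women: 10:5 and 8:4.
- Sexes pooled (main secondary-endpoint analyses): about 12-13 placebo patients per level.

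**Power per level.** Noncentral t with df = n1 + n0 − 2 and noncentrality d / √(1/n1 + 1/n0). For 16:8, √(1/16 + 1/8) = 0.433; at d = 0.8 the noncentrality is 0.8/0.433 = 1.85 on 22 df.

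| Cell | d = 0.5 | d = 0.8 | 95% CI half-width |
|---|---|---|---|
| 16:8 | 19.7% | 42.4% | 0.90 SD |
| 10:5 | 13.5% | 27.3% | 1.18 SD |
| 8:4 | 11.5% | 22.0% | 1.36 SD |

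**Chance that exactly one level is significant when the true effect is the same in both:** p1(1 − p2) + p2(1 − p1).
- No effect: 2 × 0.05 × 0.95 = 9.5%.
- Men, d = 0.5: 2 × 0.197 × 0.803 ≈ 32%.
- Men, d = 0.8: 2 × 0.424 × 0.576 ≈ 49%.
- Women, d = 0.5: 0.135 × 0.885 + 0.115 × 0.865 ≈ 22%.
- Women, d = 0.8: 0.273 × 0.780 + 0.220 × 0.727 ≈ 37%.
- Sexes pooled (12 and 13 placebo), d = 0.5 and 0.8: 41% and 48%.

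Over a wider range the figures are 18% (d = 0.3), 48% (1.0) and 37% (1.2) in men, and 14%, 46% and 50% in women. They rise and then fall in men because 2p(1 − p) peaks at 50% when p is one half.

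**With an interaction test instead.** In simulations (3,000 runs, baseline/Week 12 correlation 0.5 assumed; two- and three-level splits), a baseline-adjusted treatment-by-subgroup test at 0.05 gave a false signal in 4.5-5.6% of trials, at both d = 0 and d = 0.8. In the same simulations the separate t-tests were discordant in 9-14% at d = 0 and 37-65% at d = 0.8.

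**Precision lost by dropping adjustment.** The ratio of the ANCOVA standard error to that of unadjusted change is √((1 + ρ)/2): 0.81, 0.87 and 0.92 for assumed correlations ρ of 0.3, 0.5 and 0.7.

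**Expected width of the interaction interval (ρ = 0.5, so factor 0.866)**
- Men: √(2 × (1/8 + 1/16)) = 0.612; 0.612 × 0.866 × 2.017 (43 df) = 1.07 SD.
- Women: √(1/5 + 1/10 + 1/4 + 1/8) = 0.822; 0.822 × 0.866 × 2.074 (22 df) = 1.48 SD.

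**The case against.** Several stronger readings are tempting, and the documents do not support them.

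- **That significant or not significant is the only output.** It is not. SAP 7.3 and item 3 of 8.1.1-8.1.9 keep the between-arm difference with its 95% CI in every level. What is missing is adjustment, and any estimate of the difference between levels.
- **That chance findings will be declared effect modification or used to choose the next trial's population.** Neither document says so. This is a phase 2a study with a descriptive primary analysis. The risk is misreading, and the SAP has no rule against it.
- **That cells hold only a handful of placebo patients throughout.** That fits BCI/PIP1, the by-sex repeats and uneven splits. Pooled-sex secondary analyses have about 12-13 per level on an even split.
- **That BCI/PIP1 carry 96 separate chances of a false positive.** Age (2 levels), IPSS (3), QOL (3) and post void residual (4) make 12 levels per sex, or 24 comparisons. Each is seen up to four times (change and percentage change, FAS and PPS), and the residual categories overlap. Under no effect, 24 × 0.05 = 1.2 comparisons would be expected to be significant by chance.
- **That no interaction analysis exists anywhere.** SAP section 12 says that only the major items are listed and that a separate report analysis plan holds the rest. The defensible statement is that the SAP specifies none.

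Two objections limit the gain. The planned t-tests already use change from baseline. An interaction estimate at this size will also rarely settle the question: for a 0.8 SD interaction, power is about 31% in men and 19% in women on even splits (ρ = 0.5 assumed). Both stand. They are reasons to label the results exploratory. They do not make separate tests a better guide to whether effects differ.

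**Conclusion.** The concern holds as a weakness of method in the subgroup analyses. Within age, severity and post-void-residual levels the SAP relies on unadjusted comparisons and specifies no estimate of the between-level difference in effect. With a common true effect of 0 to 0.8 SD, an even split would show one significant half and one non-significant half in about 10-49% of trials in men and 10-37% in women.

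These figures rest on assumed effect sizes, even splits, two-sided 0.05 and the full target enrolment. They describe a single split of a single endpoint, so discordance is possible in any one comparison, not certain. Subgroup conclusions are affected; the primary analysis is not.

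**What to change.** In SAP 7.3 and 8.1.11-8.1.13, add a model that estimates the interaction:

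1. For BCI in men and PIP1 in women, separately, fit ANCOVA at Week 12 with baseline, treatment, subgroup and treatment-by-subgroup.
2. Do the same for the Week 12 value of each secondary endpoint, adding sex where the sexes are pooled. A full treatment-by-visit-by-subgroup MMRM is too large for the by-sex repeats.
3. Treat the post-void-residual cuts at 50 mL and 100 mL as two separate dichotomies, since the listed categories overlap and cannot form one factor. Merge severity classes that are too sparse, deciding this before unblinding.
4. Report the adjusted difference in each level and the interaction estimate, both with 95% CI. Label them exploratory, and state that within-level p-values will not be used as evidence of a subgroup difference.
5. State whether the OABSS severity analysis covers the primary endpoint.

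**Cost.** SAP wording and modest programming, with no new data. For uroflowmetry (8.1.3) and KHQ (8.1.8) this adds a model rather than restoring one, because neither has an adjusted analysis planned. The interaction intervals will be wide, with half-widths of roughly 1.0-1.1 SD in men and 1.4-1.5 SD in women on even splits.

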8.1.13 Analysis by Post Void Residual

The following analyses will be performed. The same analyses will be performed by sex.

- Analyses of the primary and secondary endpoints excluding analysis of covariance/analysis using an MMRM and scatter plots (7.3 and 8.1.1 to 8.1.9) will be performed by post void residual measured by ultrasonography (< 50 mL, \geq 50 mL, < 100 mL, and \geq 100 mL) at baseline (Week 0).

8.1.14 Analysis by Appearance of Bladder Involuntary Contraction

The following analyses will be performed in the PPS. The same analyses will be performed by sex.

- Analyses of the primary and secondary endpoints (7.3 and 8.1.1 to 8.1.5) will be performed by appearance of bladder involuntary contraction. However, frequency tabulation of the appearance of bladder involuntary contraction and analysis of covariance/analysis using an MMRM in 8.1.1, 8.1.4, and 8.1.5 will not be performed.

8.1.15 Analysis of UDS Data Subset

The following analyses will be performed in the PPS. The same analyses will be performed by sex. Cases raising queries were pointed out at the urodynamic study data review meeting, and as a result of consideration by the case review committee, the appropriate urodynamic study evaluation set, with cases raising queries excluded, was taken to be the UDS data subset.

- Analyses of the primary and secondary endpoints (7.3 and 8.1.1 to 8.1.5) will be performed in the UDS data subset. However, frequency tabulation of the appearance of bladder involuntary contraction and analysis of covariance/analysis using an MMRM in 8.1.1, 8.1.4, and 8.1.5 will not be performed.

8.2 Analysis of Administration Status

The following analyses will be performed by treatment group in patients treated in the observation period and patients treated in the treatment period.

8.2.1 Study Drug Administration

Summary statistics for administration status (total dose and total duration of administration) will be presented for each patient.

8.2.2 Status of Administration Completion

- Summary statistics for treatment compliance will be calculated for each patient.
- Whether patients are discontinued from the study and the reasons for discontinuation will be tabulated.

8.3 Safety Analysis

The following analyses will be performed for each treatment group in patients treated in the treatment period.

8.3.1 Adverse Events and Adverse Reactions

The following analyses will be performed at each time point.

- The numbers of patients who experienced adverse events and the incidences of adverse events will be displayed. Similar analysis will be performed for adverse reactions. Similar analysis will also be performed by age (≥ 65 years and < 65 years). In addition, similar analysis will be performed by age (≥ 75 years and < 75 years).
- For each adverse event item, the numbers of patients who experienced adverse events and the incidences of adverse events will be displayed. Similar analysis will be performed for adverse reactions. Similar analysis will also be performed by age (≥ 65 years and < 65 years). In addition, similar analysis will be performed by age (≥ 75 years and < 75 years).
- For each adverse event item, the numbers of patients who experienced adverse events and the incidences of adverse events will be displayed by severity. Similar analysis will be performed for adverse reactions.
- The incidence of adverse events in the treatment period will be presented by time of onset (at or before Week 2 of the treatment period; after Week 2 of the treatment period and at or before Week 4 of the treatment period; after Week 4 of the treatment period and at or before Week 8 of the treatment period; after Week 8 of the treatment period and at or before Week 12 of the treatment period; after Week 12 of the treatment period; and follow-up observation). Similar analysis will be performed for adverse reactions.
- All adverse events that occurred from the start of study treatment to the end date of the follow-up observation will be listed by the adverse event variable of each patient, together with the adverse event term, severity, date of onset, action, outcome, causal relationship with the study drug, and comments.
- The incidence of serious adverse events will be calculated. Similar analysis will be performed for adverse reactions.
- The incidence of adverse events leading to discontinuation/dose interruption will be calculated. Similar analysis will be performed for adverse reactions.

8.3.2 Laboratory Test Values

If the measured values of each laboratory test parameter (quantitative parameter) include " \leq ," the analysis will be performed using the numerical values excluding inequality.

- For each laboratory test parameter (quantitative parameter), the time course of measured values will be shown in graphs.
- Summary statistics for the laboratory test parameters (quantitative parameters) at each time point will be calculated.
- The frequency of each laboratory test parameter (urinalysis parameter) at each evaluation time point will be tabulated.

8.3.3 12-lead Electrocardiogram

- For QTcF interval and heart rate, summary statistics for measured values will be calculated for each evaluation time point.
- For QTcF interval and heart rate, summary statistics for the change in the measured value at each evaluation time point relative to directly before the start of administration of the investigational drug for the treatment period will be calculated.
- The measured value of QTcF interval at each evaluation time point will be divided into categories (≤ 450 msec, > 450 msec and ≤ 480 msec, > 480 msec and ≤ 500 msec, and > 500 msec), and the frequency of each category will be tabulated.
- For QTcF interval, the change in the measured value at each evaluation time point relative to directly before the start of administration of the investigational drug for the treatment period will be divided into categories (≤ 30 msec, > 30 msec and ≤ 60 msec, and > 60 msec) and their frequencies were tabulated.
- A list of patients with abnormal 12-lead electrocardiogram changes will be prepared.

8.3.4 Blood Pressure, Pulse Rate, and Body Temperature

- Summary statistics for blood pressure, pulse rate, and body temperature at each time point will be calculated.
- For blood pressure and pulse rate, summary statistics for the change in the measured value at each evaluation time point relative to directly before the start of administration of the investigational drug for the treatment period will be calculated.

9. Other Analyses

